### **Registry Procedure-related**

The registry procedure (and not the device or other adjunctive procedure) caused or significantly contributed to the adverse event.

#### **Registry Disease-related**

The adverse event was a result of the underlying disease progression for which the registry procedure is being performed, and not the device or procedure. Within the dialysis cohort, adverse events attributed to a cannulation procedure should be classified as registry disease-related.

#### **Not-related**

An adverse event which cannot be attributed to the device, procedure, or disease.

MD133246 Protocol Template

## **Unknown relationship**

The relationship of the adverse event to the device, procedure, or disease cannot be determined.

#### 9.1.2. Adverse Event Classification

Each AE will be assessed by the Investigator to determine if it is Serious or Nonserious, as defined below, per ISO14155.

#### Serious Adverse Event

A serious adverse event is an adverse event that

- Led to death
- Led to serious deterioration in the health of the subject that resulted in:
  - o A life-threatening illness or injury,
  - o A permanent impairment of a body structure or a body function.
  - o Hospitalization or prolongation of patient hospitalization, or
  - Medical or surgical intervention to prevent life-threatening illness or injury or permanent impairment to a body structure or a body function
  - o Chronic disease
- Led to fetal distress, fetal death, or congenital physical or mental impairment or birth defect.

Any AE that does not meet the definition of a SAE will be considered Non-serious. Planned hospitalization for elective procedure without serious deterioration in

**NOTE:** Emergency room visits and 23-hour observations may not constitute hospitalization.

### 9.1.3. Adverse Event Reporting and Coding

health is not considered serious.

Considering the retrospective nature of the registry only AEs already documented in the subject's medial record will be reported on the appropriate CRF.

No follow-up related to the open adverse event in order to obtain new information is required for this registry.

The investigator at each site is ultimately responsible for reporting AEs to the sponsor.

The following information on each reported AE will be collected:

- Adverse event name
- Adverse event onset date
- Relationship
- Classification serious or non-serious
- Outcome
- Resolution date

Adverse events will be coded using the Medical Dictionary for Regulatory Activities (MedDRA).

Adverse event submission guidelines:

- Adverse event reporting begins once the patient is enrolled in the registry (ICF signed or waived). All adverse events should be reported from index procedure through registry completion / discontinuation.
- Provide a diagnosis if possible. If unable to provide a diagnosis, report the symptoms as separate events. Adverse events should be reported using the full name without abbreviations or narratives.
- Adverse events ongoing at registry completion / discontinuation should be left as "ongoing" on the AE case report form.
- Medical condition and adverse event observed at the time of treatment will be part in the medical history of the patients. Adverse events will be reported in the EDC only if they become serious or increase in intensity, or if a worsening of a baseline condition.

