# 3.3. Registry Endpoint(s)

### 3.3.1. Definitions

Outcome	Definition
Primary Patency	
Aortic Aneurysm / PAD Cohort	Patency of the study graft without additional or secondary surgical or endovascular procedures to maintain or restore flow to the graft. The only exceptions that do not disqualify the graft for primary patency are procedures performed for disease beyond the graft and its two anastomoses.
Dialysis Access Cohort	Interval following intervention until the next access thrombosis or repeated intervention.
Secondary Patency	
Aortic Aneurysm / PAD Cohort	Patency of the study graft with additional or secondary surgical or endovascular procedures to restore flow to the graft after occlusion or stenosis of the graft or its anastomoses  The only exceptions that do not disqualify the graft for secondary patency are procedures performed for disease beyond the graft and its two anastomoses
Dialysis Access Cohort	Patency of the study graft from the time of access creation or placement until access abandonment
Limb Salvage	Freedom from an amputation above the level of the ankle of the index limb
Amputation Free survival	Freedom from an amputation above the level of the ankle of the index limb or all cause death
Device-related seroma or infection PAD Cohort	Clinical evidence of an infectious process in the direct vicinity of the access site or distal to the treated vascular site or seroma classified by the registry investigator as primarily related to the registry device

Device-related infection requiring reoperation PAD Cohort	Clinical evidence of an infectious process in the direct vicinity of the access site or distal to the treated vascular site classified by the registry investigator as primarily related to the registry device and required surgical intervention
Device-related infection  Dialysis Access Cohort	Clinical evidence of an infectious process in the direct vicinity of the access site classified by the study investigator as primarily related to the study device
Survival	All Cause survival
Device-related Adverse Events	Any untoward medical occurrence classified by the registry investigator as primarily related to the registry device

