### 3.3.3. Secondary Endpoints

- 3.3.3.1. Peripheral Artery Disease Cohort
  - Limb Salvage through 1 year
  - Amputation-free survival through 1 year
  - Device-related Adverse Events through 1 year
  - Device-related infection requiring reoperation through 5 years
  - Primary Patency through 1 year
- 3.3.3.2. Dialysis Access Cohort
  - Primary patency through 1 year
  - Device-related adverse events through 1 year

No secondary endpoints have been identified for the Aortic Aneurysm Cohort.

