# 8.0 Data Sets, Tables, Figures, and Listings

This section includes a list of the minimal planned statistical outputs, including tables, listings and figures which are to be created for the regulatory reports defined in the protocol. A different selection of tables, listings, and figures can be created for all other reporting efforts (Annual Reports etc.) as deemed necessary.

- 8.1 Analysis Tables
  - Summary of Subject Demographics by cohort
  - Summary of Medical History by cohort
  - Summary of concomitant medication by cohort
  - Summary of procedural details and assessments by cohort
  - Summary of discharge details by cohort
  - Summary of the devices used by cohort
  - Summary of follow-up, subject availability by visit with counts and percentages.
  - Kaplan-Meier estimate of the Device-related seroma or infection through 5 years in the PAD cohort
  - Kaplan-Meier estimate of the Secondary Patency (revascularization) through 5 years in the PAD cohort
  - Kaplan-Meier estimate of Survival through 5 years in the AA cohort
  - Kaplan-Meier estimate of the Primary Patency through 5 years in the AA cohort
  - Kaplan-Meier estimate of the Device-related infection through 2 years in the DA cohort
  - Kaplan-Meier estimate of the Useable access circuit(reported as secondary patency) through 2 years in the DA cohort
  - Kaplan-Meier estimate of the Limb Salvage through 1 year in the PAD cohort
  - Kaplan-Meier estimate of the Amputation-free survival through 1 year in the PAD cohort
  - Kaplan-Meier estimate of the Device-related Adverse Events through 1 year in the PAD cohort
  - Kaplan-Meier estimate of the Device-related infection requiring reoperation through 5 year in the PAD cohort
  - Kaplan-Meier estimate of the Primary Patency through 1 year in the PAD cohort

- Kaplan-Meier estimate of the Device-related Adverse Events through 1 year in the DA cohort
- Kaplan-Meier estimate of the Primary Patency through 1 year in the DA cohort
- Summary of the Device-related SAEs by cohort
- Summary of the Device-related death by cohort
- Summary of the procedure-related death by cohort
- Summary of the procedure-related SAE by cohort
- Summary of Repeat Interventions by cohort
- Summary of Freedom from Limb Salvage by cohort
- Summary of Device or Procedure Related Serious Adverse Events by cohort
- Summary of Adverse Events by MedDRA SOC, HLT, PT and Follow-up Interval (Number of Subjects, Number of Subjects with AEs, Number of AEs, at Procedure) by cohort

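### Protocol section 9.1.3 has two conflicting recording rules, so sites could file non-serious events that start during the implant procedure as medical history and not as adverse events

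*Protocol*

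**What the plan says.** Two bullets under the submission guidelines in Protocol section 9.1.3 govern what goes on the adverse event form. The first states: "All adverse events should be reported from index procedure through registry completion / discontinuation". The last states: "Medical condition and adverse event observed at the time of treatment will be part in the medical history of the patients". It then adds: "Adverse events will be reported in the EDC only if they become serious or increase in intensity, or if a worsening of a baseline condition".

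The endpoint that depends on this form is defined in Protocol section 3.3.1 as "Any untoward medical occurrence classified by the registry investigator as primarily related to the registry device", with no restriction by timing or seriousness. Protocol section 3.3.3 lists it, through 1 year, as a secondary endpoint for the PAD and Dialysis Access cohorts. For the third cohort that section says: "No secondary endpoints have been identified for the Aortic Aneurysm Cohort".

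Other parts of the plan treat procedural events as adverse event data. Protocol section 9.1.1 has a relationship class for events where "The registry procedure (and not the device or other adjunctive procedure) caused or significantly contributed to the adverse event". SAP section 8.1 plans an all-event summary by cohort that includes "Number of AEs, at Procedure".

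**The concern.** The last bullet names adverse events alongside medical conditions, and nothing in it confines either to onset before the procedure. A coordinator reading the chart of a patient who had a minor, non-serious event during implantation has two instructions. One says to report it. The other says to put it in medical history unless it becomes serious or worsens. With up to 9 sites and no clinical event committee (SAP section 4.1), nothing in the plan ensures that sites resolve this the same way.

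What is at stake is the count of non-serious procedural events in the adverse event tables of all three cohorts, and the 1-year device-related adverse event estimate in two of them. Section 9.1.3 lists onset date, relationship and seriousness as items collected for each reported adverse event. Neither document says that a medical-history entry carries them. An event filed there might therefore not be identifiable at analysis as device-related or as arising on the day of implant.

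**Working it through.** The documents give no figure for this point, so the main check is to follow each kind of event through the two readings of the last bullet.

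**Step 1. Which events change place.**

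| Event | Time of treatment includes the implant procedure | Time of treatment means status before the procedure |
|---|---|---|
| Condition present beforehand, unchanged | Medical history | Medical history |
| Starts during the procedure, non-serious, does not worsen | Medical history only | Adverse event form |
| Starts during the procedure, serious or later intensifies | Adverse event form | Adverse event form |
| Starts after the procedure | Adverse event form | Adverse event form |

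Only the second row differs.

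**Step 2. Which outputs that row reaches.**

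- The all-event table in SAP section 8.1, in every cohort, including its at-procedure count. The corresponding serious-event table lists no at-procedure item, so the all-event table is where non-serious procedural events would appear.
- Device-related adverse events through 1 year in PAD and Dialysis Access, but only for events whose single primary relationship (Protocol section 9.1.1) is to the device. Events rated procedure-related never count towards this endpoint.
- Primary endpoints (patency, survival, device-related infection or seroma): a non-serious event confined to the implant procedure is unlikely to be one of these. Patients with known or suspected infection at implant are excluded by Protocol section 4.3.1.

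**Step 3. The denominator.** The plan sets 72 patients per device in PAD and Dialysis Access. This reproduces: with an exact (Clopper-Pearson) 95% interval, 72 is the smallest size giving a half-width of at most 12% at a rate of 55%, and the half-width there is 11.97%. The sample size does not depend on the present point; only the 72 is used below.

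**Step 4. Effect per patient.** Let m be the number of patients in a 72-patient group whose only device-related event in year 1 was misfiled. With complete follow-up to 1 year, the reported proportion falls by m/72:

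- m = 0: no change
- m = 1: 1/72 = 1.4 points
- m = 2: 2/72 = 2.8 points
- m = 4: 4/72 = 5.6 points

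A patient with another device-related event in year 1 that is entered on the form still counts, so the unit is patients and not events.

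**Step 5. A hypothetical example.** The documents give no rate for these events. Purely as an assumption, suppose 7 of 72 patients truly have a first-year device-related event:

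| m | Reported | Exact 95% interval |
|---|---|---|
| 0 | 7/72 = 9.7% | 4.0% to 19.0% |
| 1 | 6/72 = 8.3% | 3.1% to 17.3% |
| 2 | 5/72 = 6.9% | 2.3% to 15.5% |
| 4 | 3/72 = 4.2% | 0.9% to 11.7% |

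**The case against.** The strongest reply is that the bullet is about baseline status. The eligibility criteria in Protocol sections 4.3.1, 4.3.2 and 4.3.4 use the same phrase for what the patient had on arrival, such as pregnancy, a coagulation disorder or a stroke in the preceding weeks. The bullet's own exception speaks of worsening of a baseline condition. The procedure-related class and the at-procedure table show that procedural events were meant to be entered. On that reading nothing is lost. I accept this as the probable intent. It does not settle the matter, because the text does not say so and this reading leaves the separate mention of adverse events without a clear meaning.

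Several stronger readings are tempting, but the documents do not support them.

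- A reader might infer that all intra-procedural events are dropped. The bullet's exception keeps serious and worsening events on the form.
- A reader might take the exception, which states no time limit, to remove non-serious events throughout follow-up. It sits inside the bullet on events at treatment, and the form has a serious or non-serious field for each event, so this is not the natural reading.
- A reader might infer that misfiled events cannot be recovered. Medical history is also recorded in the database (Protocol section 5.8.2) and tabulated (SAP section 8.1). Misfiling is a supported risk. Irrecoverable loss is not shown, because the case report form is not among the documents.
- A reader might assume 3 to 5 lost events per 72 patients and quote a bias of 4.2 to 6.9 points. No event rate in the documents supports that count. It treats events as patients and leaves out zero, which is the result on the likely reading.

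**Conclusion.** The contradiction within Protocol section 9.1.3 is real on its plain wording, and it also clashes with the unrestricted definition of device-related adverse events and with the SAP's at-procedure count. Its reach is narrow: non-serious, non-worsening events that start during the implant procedure. The only endpoint it touches is a secondary one, in two of the three cohorts. The Aortic Aneurysm cohort is affected only in its descriptive tables.

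The effect cannot be sized from the documents. It is zero if sites read the bullet as covering pre-existing conditions. Otherwise it is about 1.4 points per affected patient, assuming a group of 72 with complete 1-year follow-up and no other device-related event in that patient. Any error would be an undercount and could vary by site. It is an inconsistency that should be corrected, and it does not put the primary results in doubt.

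**What to change.** Replace the last bullet of Protocol section 9.1.3 with wording such as: *Conditions with onset before the start of the index procedure are medical history and are reported as AEs only if they become serious or worsen after the start of the index procedure; any event with onset during or after the index procedure is reported as an adverse event, whatever its seriousness.*

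This removes the undefined time of treatment, ties the exception to pre-existing conditions only, and agrees with the first bullet and with SAP section 8.1. Add a matching line to the case report form guidance. The cost is one reworded bullet, that line, and slightly more adverse event entries. The change concerns data recording only.

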## 9.1.4. Subject Death

In this registry, death is not considered an AE, but rather the outcome of an AE. An ongoing AE at the time of death or registry withdrawal will remain categorized as ongoing.

# 9.2. Unanticipated Serious Adverse Device Effects (USADE)

The sponsor is required to notify the appropriate regulatory agencies per local requirements of any USADE. Therefore, if a complication occurs that the investigator believes may be a potential USADE, the site should immediately contact the sponsor and EC to determine reporting requirements.

# 9.3. Device Deficiency

Device deficiencies are defined as any inadequacy in the identity, quality, durability, reliability, safety, or performance of an investigational device, including malfunction, use errors, or inadequacy in information supplied by the manufacturer.

All device deficiencies – even those that could have led to a SAE should be reported to the Sponsor immediately.

The following information on each reported deficiency will be collected:

- Description of deficiency
- Date of occurrence
- Batch code and lot number of the affected device
- Related subject AE information (if applicable)

Due to the retrospective approach, any device deficiency may have already been reported as part of the hospital's routine via Product Surveillance Group procedures. To close any potential gaps, sites are asked to report all device deficiency in the EDC.

# 10. Statistical Analysis

# 10.1. Registry Hypotheses

No formal statistical hypothesis is planned for testing in the study. Separate primary and secondary outcomes will be measured along with 95% confidence intervals for each cohort using Exact Binomial method. The analysis of the primary endpoint will be descriptive in nature.

Page 30 of 43

# 10.2. Sample Size Assumptions

The sample size for the study is estimated using the desired width of the 95% confidence interval. It is assumed that for PAD and Dialysis cohorts, if the estimated percentage of the primary outcome is around 55%, the half-width of the confidence interval would be 12%. Similarly, for the Aortic Aneurysms, considering the primary outcome to be around 32%, the sample size of 65 subjects would allow the half-width of the confidence interval to be lower than 12%.

Cohort	Endpoint Used for Sample Size Calculation, Assumed Rate	Sample Size
PAD	≥ 56% Secondary patency (revascularization) at 5 years	72 Patients (per device)
Aortic Aneurysm	≥ 33% survival at 5 years	65 Patients
Dialysis Access	≥ 55% secondary patency through 2 years	72 Patients (per device)

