### 5.12. Subject Lost to Follow Up

No subject lost to follow up are expected in this registry. According to General Exclusion criterion #1, subjects with no follow-up after treatment should not be included in the registry. All subjects that complete at least one follow-up after treatment will be enrolled.

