# 10.3. Sample Size Determination

The sample is calculated assuming the Binomial Exact 95% confidence interval would be constructed for the primary outcomes using the above assumptions. The subjects for which the primary outcomes cannot be determined will be considered missing in the analysis.

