# 10.6.4. Statistical Analysis of Primary Endpoint(s)

Analysis for the primary endpoints will be presented with confidence intervals. Missing data at the time of analysis will not be imputed.

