### Table 2. Sample sizes

Cohort	Endpoint Used for Sample Size Calculation, Assumed Rate	Sample Size
PAD	≥ 56% Secondary patency (revascularization) at 5 years	72 Patients (per device)
Aortic Aneurysm	≥ 33% survival at 5 years	65 Patients
Dialysis Access	≥ 55% secondary patency through 2 years	72 Patients (per device)

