#### ii. Analysis Populations

This study consists of five different analyses populations, defined by indication/disease type and device used. Separate analysis will be performed for each patient population.

- a. PAD patients treated with any
- b. PAD patients treated with
- c. Aortic Aneurysm patients treated with any
- d. Dialysis Access patients treated with any
- e. Dialysis Access patients treated with any
- iii. Pooling of Data

Clinical use is not expected to differ significantly between study sites. As such, there is no anticipated concern in pooling the data from different sites for analysis. However, separate analysis will be performed to show the consistency of safety and effectiveness by gender and age for the primary outcomes.

i) Statistical Analysis of Primary Endpoint(s)

Analysis for the primary endpoints will be presented with confidence intervals. Subjects with missing information on the primary outcomes will not be included in the analysis for the primary endpoint.

ii) Statistical Analysis of Secondary Endpoint(s)

Analysis for the secondary endpoints will be presented with confidence intervals. Subjects with missing information on these outcomes will not be included in the analysis.

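### Are the 12-point confidence-interval half-widths in Protocol 10.2 and SAP 2.6 overstated because undetermined outcomes are dropped and the aortic rate is a floor?

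*Protocol*

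**What the plan says.** Each cohort is sized on the width of a two-sided 95% exact binomial interval for one endpoint (Protocol 10.2 and 10.3; SAP 2.6, 2.7 and 5.0).

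- **PAD and dialysis, 72 per device:** "if the estimated percentage of the primary outcome is around 55%, the half-width of the confidence interval would be 12" percentage points. The table gives the rates as floors: 56% or more for PAD secondary patency at 5 years, 55% or more for dialysis secondary patency through 2 years.
- **Aortic aneurysm, 65 patients:** at about 32%, "the sample size of 65 subjects would allow the half-width of the confidence interval to be lower than 12" points. SAP Table 2, like the table in Protocol 10.2, gives the rate as at least "33% survival at 5 years".

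On missing outcomes, Protocol 10.3 says: "The subjects for which the primary outcomes cannot be determined will be considered missing in the analysis". Protocol 10.6.4 adds: "Missing data at the time of analysis will not be imputed". SAP 5.0, on the primary endpoints, is explicit: "Subjects with missing information on the primary outcomes will not be included in the analysis for the primary endpoint". On follow-up, Protocol 5.12 states "No subject lost to follow up are expected in this registry", resting this on the exclusion of patients with no follow-up at all, and then "All subjects that complete at least one follow-up after treatment will be enrolled". Protocol 5.10 provides for patients whose final scheduled visit is absent.

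Aortic 5-year primary patency is a primary endpoint (Protocol 3.3.2.2) but has no assumed rate and no stated half-width.

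**The concern.** Three features make the stated precision look too favourable.

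1. The sample sizes have almost no slack. 72 is the smallest n that reaches 12.0 points at 55% or 56%, and 65 is the smallest at 33%. Undetermined outcomes shrink the denominator, one follow-up visit is enough for enrolment, and replacement is described for withdrawal (5.11) and for ineligibility found after consent (5.6), not for an undetermined outcome. Having had one visit does not guarantee a known 2-year or 5-year outcome.
2. The aortic text uses 32% and the table 33% or more. Binomial intervals widen towards 50%, so a better survival result than assumed gives a wider interval, and a half-width below 12 points is soon lost.
3. One of the two aortic primary endpoints carries no precision figure.

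With no hypothesis test, interval width is the only quantitative basis for the sample size that the documents show. Protocol 2.1 mentions acceptance criteria but gives no values. If the stated widths were materially wrong, readers would expect more precision than the registry can deliver.

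**Working it through.** **Inputs.** Two-sided 95% exact binomial interval (SAP 5.0); n = 72 per device and n = 65; rates 55%, 56%, 32% and 33% (Protocol 10.2 text and table).

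**Formula.** For x successes in n, with B⁻¹(q; a, b) the beta quantile:

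- lower limit L = B⁻¹(0.025; x, n − x + 1)
- upper limit U = B⁻¹(0.975; x + 1, n − x)
- half-width = (U − L)/2

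Where a rate rather than a count is given, x = p·n.

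**Step 1: the plan's own figures.**

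| Rate | n | L to U (%) | Half-width (points) |
|---|---|---|---|
| 55% | 72 | 42.82 to 66.76 | 11.97 |
| 56% | 72 | 43.80 to 67.69 | 11.94 |
| 32% | 65 | 20.97 to 44.73 | 11.88 |
| 33% | 65 | 21.83 to 45.77 | 11.97 |

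All reproduce. A Wald interval would need only 67 patients at 55% and 59 at 32%, so the exact method was the one used for sizing.

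**Step 2: how much slack there is.**

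- At 55%: n = 71 gives 12.05, n = 67 gives 12.42, n = 66 gives 12.51. The rounded 12 survives 72 − 67 = 5 missing outcomes.
- At 56%: n = 66 gives 12.49, n = 65 gives 12.58. The rounded 12 survives 72 − 66 = 6.
- Aortic at 32%: n = 64 gives 11.98, n = 63 gives 12.08. One missing outcome still meets the below-12 statement.
- Aortic at 33%: n = 64 gives 12.07. None can be missing.

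**Step 3: larger missing shares.** The documents give no rate; 10% and 20% are assumptions.

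| Rate | No missing | 10% undetermined | 20% undetermined |
|---|---|---|---|
| 55% (n = 72, 65, 58) | 11.97 | 12.61 | 13.36 |
| 33% (n = 65, 58, 52) | 11.97 | 12.69 | 13.42 |

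The PAD and dialysis rates are floors above 50%, so better patency narrows the interval. At an assumed 65% patency, n = 67 gives 11.94, n = 65 gives 12.13 and n = 58 gives 12.86.

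**Step 4: the aortic floor, all 65 outcomes known.**

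| Survivors of 65 | Rate | Half-width (points) |
|---|---|---|
| 21 | 32.3% | 11.91 |
| 22 | 33.8% | 12.04 |
| 26 | 40.0% | 12.43 |
| 32 or 33 | 49.2% or 50.8% | 12.67 |
| 39 | 60.0% | 12.43 |
| 43 | 66.2% | 12.04 |
| 44 | 67.7% | 11.91 |

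From 22 to 43 survivors the half-width exceeds 12, by at most 12.67 − 12 = 0.67 points.

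**Step 5: aortic primary patency.** The maximum of 12.67 applies to any proportion estimated from 65 determined outcomes, so patency on all 65 would also be known to within 12.7 points.

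**The case for a change.** The case for a change is that the figures describe complete data while the plan does not secure complete data. The missing-outcome rules shorten the denominator, and the sentence expecting no loss to follow-up excludes only patients with no visit at all. The aortic point needs no assumption about missing data: the table allows any rate from 33% upwards, and between 33.8% and 66.2% the half-width is above 12. Relabelling the figures would cost only a few words.

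Much of this is accurate. No allowance for undetermined outcomes is stated, the 32% and 33% do not match, and aortic patency has no figure of its own.

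Three things limit it. First, the aortic sentence is conditional on a rate of about 32%; it does not promise a width below 12 across the table's range, and it is true at both 32% and 33%. Second, the plan works against missing outcomes: implantation lies at least 5 or 2 years before site initiation, later visits may be used, past re-interventions and deaths are collected when visit data are absent, and relatives or general practitioners are contacted where consent is waived (Protocol 4.1 and 5.10). Third, sizing each cohort on one named endpoint is a normal choice, and the table's column heading says that this was done. The PAD and dialysis safety endpoints have no precision figure either.

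SAP 8.1 lists Kaplan-Meier estimates for the same endpoints that SAP 5.0 assigns to the exact binomial method. How the two relate, and how deaths with a patent graft are counted, is a separate question that rewording the planned half-widths would not settle.

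**Conclusion.** The concern does not call for a change. Every half-width in Protocol 10.2 and SAP 2.6 is correct for the rate and sample size it is tied to. What remains is small: complete-data figures with little slack, a one-point mismatch between the aortic text and table (0.09 points of half-width, 11.97 − 11.88), and an aortic excess of at most 0.67 points for survival between 33.8% and 66.2%.

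Missing outcomes would widen the PAD and dialysis intervals at 55% by about 0.6 points if 10% were undetermined (12.61 − 11.97) and by about 1.4 points if 20% were (13.36 − 11.97). Both shares are assumptions. A much larger share would widen the intervals further, but nothing in the documents points to a particular value.

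The registry is descriptive and tests no hypothesis (Protocol 10.1). Its reported intervals will carry the achieved denominator and width. Labelling the planning figures as complete-data values, aligning 32% with 33%, or adding a patency figure would change no estimate, interval or conclusion, and none of these would alter enrolment.
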